This is a single-center, prospective, ‘open-label,’ investigator-initiated pilot study evaluating the role of continuous glucose monitor (CGM) use either alone or with remote monitoring capabilities that enable subjects to share CGM data with family and friends (whom we will call “followers” in this protocol) among women with T1DM associated with pregnancy. We hypothesize that CGM use will decrease percentage of glucose values below the target range, decrease frequency of severe hypoglycemic episodes, and increase post-prandial glucose values into the target range, with a possible reduction in A1C compared to not using CGM during pregnancy. We hypothesize that the use of remote technology (**Share™ technology**) with subject’s designated follower will decrease hypoglycemia fear and the frequency of severe hypoglycemic episodes compared to CGM use alone in pregnancy or not using CGM use in pregnancy. This study aims to improve maternal glucose management among women with T1DM with a hope to also improve health outcomes during pregnancy.

The study will enroll up to 40 patients from the Barbara Davis Center for Childhood Diabetes (BDC) Adult clinic over the age of 18 years who are pregnant (13 weeks gestation or less) or plan to become pregnant within the following 6 months. The study will also attempt to enroll up to 40 followers (one per pregnant subject) who are family members or friends of the pregnant subjects and over the age of 18 years. All subjects meeting these criteria will be invited to sign informed consent and participate in the study. All pregnant subjects will be stratified into one of three groups: (1) CGM use alone, (2) CGM use with Share™, (3) no CGM use. CGM use will be offered to all subjects, but individuals who do not want to wear a CGM will be stratified to Group 3. Stratification for Groups 1 and 2 will depend on the following: subjects and followers who have iPhones, iPads, and/or iPod touches will be placed into Group 2 which requires one of these devices to function, while all others will be placed in Group 1. All subjects will be followed for study visits with similar frequency during the pregnancy, and subjects in Groups 1 and 2 will wear the Dexcom G4 Platinum® CGM system from the first pregnancy visit until delivery. All subjects in Group 2 will also use the Share™ technology from the first pregnancy visit until delivery.

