The primary study population will consist of women at the BDC in the pre-conception and early gestational periods that are eligible for this pilot investigator-initiated CGM QI Project. Subjects will be women intending to become pregnant or within the first 13 weeks of gestation, 18 years of age or older, using MDI or CSII therapy, with any A1C level, and willing to participate in the study. There is also a no CGM comparison group of women who were pregnant around the time study enrollment began and earlier who were patients at the BDC and whose data are available retrospectively through the electronic medical record system. The secondary study population will be designated followers of pregnant patients at the BDC. Followers will be family members or friends of pregnant subjects who are willing to participate in the study.

How are subjects being recruited into the study?

Subjects will be recruited from the BDC Pregnancy and Women's Health clinic for screening, as well as the BDC Adult Clinic. During pre-conception counseling visits, women will be approached about participating in the study (if eligible). We will maintain a list of women intending to conceive within the next 6 months, ask women to come in for a pregnancy visit as soon as pregnancy is confirmed, and stratify women into 1 of 3 groups described below. If after 6 months a woman on the list has not yet come in for a pregnancy visit, we will contact her to inquire if she still plans to conceive (keep subject on the list) or not (remove from list).

Women who have their first pregnancy visit at the BDC at 13 weeks of gestation or less will be screened for the study. If eligible and interested in participating, after signing the informed consent, women will be stratified to either CGM use alone (Group 1) or CGM use with Share™ (Group 2). As Share™ requires specific device use, Group 1 subjects will be women who do not have an iPhone, iPad, or iPod touch or whose main follower does not have an iPhone, iPad, or iPod touch. Group 2 subjects will be women who have an iPhone, iPad, or iPod touch and whose main follower also has an iPhone, iPad, iPod touch, or other compatible device for downloading the Follower app. If eligible to participate but not interested in using a Dexcom CGM, women will be invited to sign informed consent so that we may follow their

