outcomes over the course of the pregnancy while diabetes control is managed per usual care (Group 1 for women using a non-Dexcom CGM such as Medtronic Enlite CGM or Group 3 for no CGM use). A PRA will maintain an active list of individuals and will update the list continuously as women are assigned into groups. All subjects will have similar clinical visits throughout the pregnancy.

Subjects stratified to Group 2, CGM use with Share™, will be asked to designate followers who will be able to view glucose trends and receive alerts for high or low sensor glucose values on an iPhone, iPad, iPod touch, and/or other compatible device. While multiple followers are allowed, one will be the main follower and will be invited to sign informed consent at the screening visit or within the first two months of each subject's study participation. Subjects stratified into Groups 1 and 3 will be asked to designate a main follower who may be aware of a subject's extreme glucose values (lows or highs) through contact with her and who may intervene on her behalf in such cases and will be invited to sign informed consent at the screening visit or within the first two months of each subject's study participation.

What are the treatment groups?

There will be three 'open-label' treatment arms consisting of routine care in the Pregnancy and Women's Health clinic at the BDC (no CGM use), an intervention arm using the Dexcom G4 or G5 Platinum® CGM system during pregnancy, and an additional treatment arm using the Dexcom G4 or G5 Platinum® CGM system with Share™ remote monitoring capabilities during pregnancy. As this is a non-randomized study and most women will opt to be in the Dexcom alone or Dexcom Share groups, we will include pregnant no CGM users identified through a retrospective chart review into the no CGM arm of the study.

How many subjects per treatment arm?

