The primary endpoints are glucose variability and changes detected by hypoglycemic fear survey. We will measure indices of glucose variability (mean glucose \pm SD, % of glucose within/above/below target ranges, J Index, High Blood Glucose Index [HBGI], Low Blood Glucose Index [LBGI], Mean Amplitude of Glycemic Excursions [MAGE], CONGA_n) throughout pregnancy using the SMBG 7-point profiles for one week taken once per trimester. Hypoglycemic fear survey results will be assessed once monthly over the pregnancy. We will compare outcomes within individuals over time and between individuals of the different study arms. We will test whether outcomes differ between women using Dexcom alone and women using Dexcom with Share™ using interaction terms, and will stratify analyses if differences by group are greater than 10 mg/dL in mean glucose levels are detected. Since SMBG logs will be taken at multiple time points over the pregnancy and since CGMs will be worn continuously for the duration of each pregnancy, linear mixed models will be used to assess changes in outcome measures (GV, time spent in target below or above target) over time in each trimester of pregnancy. We will use linear mixed models to assess changes in the hypoglycemic fear survey in each month of the pregnancy. Secondary endpoints include A1C differences among study arms. Improvement in glycemic variability parameters with a possible reduction of A1C by 0.3%, measured as the difference of the mean A1C laboratory values of the arms of the study between baseline (0-3 months, first trimester), second trimester (3-6 months), and third trimester (6 to 9 months). Mixed models account for missing data, allow for an unstructured covariance matrix for repeated measures, and account for inter-subjects correlation of measurements. Secondary outcomes will be used

in the same mixed models. Differences in frequency of low alert glucose rates, high alert glucose rates, and interventions for low or high glucose values among the followers for each study arm will be analyzed with student t-tests. A p-value < 0.05 will be considered significant, and we will perform statistical analyses with SAS software (version 9.3, SAS Institute, Cary NC).

Publication Strategy:

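### Women who decline Dexcom but wear another CGM are assigned to Group 1, and the plan does not say how they enter the comparison of Dexcom alone with Dexcom plus Share

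*Combined protocol and SAP*

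**What the plan says.** The allocation rule is under *How are subjects being recruited into the study?* It covers women who are eligible but do not want the study device: "If eligible to participate but not interested in using a Dexcom CGM, women will be invited to sign informed consent". They are followed while "diabetes control is managed per usual care", and are then split by what they wear: "Group 1 for women using a non-Dexcom CGM such as Medtronic Enlite CGM", and Group 3 for those with no CGM.

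Other sections describe Group 1 as a Dexcom arm:

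- The opening summary says that "subjects in Groups 1 and 2 will wear the Dexcom G4 Platinum® CGM system from the first pregnancy visit until delivery".
- *What are the treatment groups?* defines the CGM-alone arm as "an intervention arm using the Dexcom G4 or G5 Platinum® CGM system during pregnancy" and expects that "most women will opt to be in the Dexcom alone or Dexcom Share groups".
- *Stratification, Visit 2* supplies Dexcom sensors, and a Dexcom unit where needed, to women in Groups 1 and 2. It makes no exception for women who declined Dexcom.

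The *Statistical Analysis Plan* adopts intention to treat, compares the study arms, and then states: "We will test whether outcomes differ between women using Dexcom alone and women using Dexcom with Share". It has no rule to flag, exclude, adjust for or separately report women on another CGM.

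Other text is neutral on brand. The opening summary and the recruitment section label Group 1 simply as CGM use alone. The secondary A1C outcome and the stated goal of the study also speak of CGM with or without remote monitoring, without naming a maker.

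**The concern.** Two routes lead into Group 1. The usual one is that the woman or her main follower lacks a suitable Apple device. The second is that she refused Dexcom and wears something else, whatever phone she owns. Women who enter by the second route do not receive the study device or use its supplied sensors, and they are selected by a device preference.

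The study hypothesizes that Share lowers hypoglycemia fear and severe hypoglycemia relative to CGM alone. Group 1 against Group 2 is the comparison that addresses this. If women on another device are counted in Group 1, the comparison also carries brand, sensor supply and self-selection. If they are not counted, the plan does not say so, and the choice would be made with the data in hand. The pilot is meant to inform a much larger study, so the Share comparison should have a stated population.

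**Working it through.** **1. The plan's own figures.** The *Statistical Analysis Plan* gives 40 women and 20% drop-out: 40 × 0.20 = 8, leaving 40 − 8 = 32. *How many subjects per treatment arm?* anticipates 10 + 20 + 10 = 40. Both reproduce, and this point disputes neither. There is no power calculation to check.

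**2. Two readings of the SAP contrast.**

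- *By arm.* Under intention to treat, a woman assigned to Group 1 is analysed in Group 1. The treatment-groups section identifies that arm with Dexcom alone, so a woman on another CGM counts on the Dexcom-alone side.
- *Literally.* She does not use Dexcom, so she is in neither side of the contrast, and no other analysis of her data is described.

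The documents do not choose between the two. Each leaves something to settle.

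**3. Weight of each woman.** With 10 expected in Group 1, each is 1/10 = 10% of the arm.

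**4. Illustrative shift.** Let k be the number of non-Dexcom users among the 10, and b their difference in mean glucose from the Dexcom-alone women. The documents give neither, so both are assumptions. The shift in the Group 1 mean, and so in the contrast, is (k/10) × b:

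- k = 1, b = 10 mg/dL: 0.1 × 10 = 1 mg/dL
- k = 3, b = 20 mg/dL: 0.3 × 20 = 6 mg/dL
- k = 5, b = 30 mg/dL: 0.5 × 30 = 15 mg/dL

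The plan's trigger for stratifying analyses is a 10 mg/dL group difference in mean glucose. Mixing alone would produce that only if b = 10/(k/10): 33 mg/dL for k = 3, or 20 mg/dL for k = 5.

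**5. Precision cost of restricting the contrast to Dexcom users.** With equal variances, the standard error changes by the factor sqrt[(1/(n1 − k) + 1/n2) / (1/n1 + 1/n2)].

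| n1 v n2 | k | Calculation | Factor |
|---|---|---|---|
| 10 v 20 | 2 | sqrt(0.1750/0.1500) | 1.08 |
| 10 v 20 | 3 | sqrt(0.1929/0.1500) | 1.13 |
| 8 v 16 | 2 | sqrt(0.2292/0.1875) | 1.11 |
| 8 v 16 | 3 | sqrt(0.2625/0.1875) | 1.18 |

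The 8 v 16 rows apply the planned 20% drop-out evenly (10 × 0.8 and 20 × 0.8) and assume that the k women are among the completers.

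**6. Scale of that cost.** Assuming 80% power, two-sided 0.05 and a normal approximation, the detectable difference is (1.960 + 0.842) × sqrt(1/10 + 1/20) = 1.09 SD for 10 v 20. For 7 v 20 it is 2.802 × sqrt(1/7 + 1/20) = 1.23 SD.

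**The case against.** A reader might infer that the SAP analyses Group 1 as Dexcom alone, so that the contrast is contaminated as planned. The documents do not go that far. The SAP never equates the two, and taken literally its wording already leaves out users of other devices. The brand-neutral labels also give these women a legitimate place in Group 1 if the question is CGM without Share. That objection stands, and it makes renaming the arm as good a remedy as excluding the women.

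A reader might also infer that Group 1 against Group 2 would isolate Share once these women were removed. It would not. The two groups differ by Apple device ownership in the woman and her follower, and the protocol itself lists the lack of randomization as a weakness.

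The difference in care is easily overstated. Visits are similar across groups, all women are asked to test at least 7 times a day, and all three groups receive diabetes education. What remains is brand, supplied sensors and device preference.

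The SAP takes its glucose-variability indices from the self-monitored 7-point profiles, so sensor brand does not distort those values. It could affect the CGM-derived indices, which the opening summary also lists under the primary outcome.

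Finally, the protocol expects most women to choose the Dexcom groups, so few or no women may be affected. None of this removes the conflict between the allocation rule and the arm definition.

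**Conclusion.** The conflict is real, and no other section resolves it. The recruitment rule sends women who declined Dexcom and wear another CGM to Group 1, while the opening summary, the treatment-group definition and the SAP contrast describe that side as Dexcom wearers. By arm, the contrast mixes Share with brand, sensor supply and refusal of the study device. Literally, these women have no stated place in it.

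The only size that the documents support is that each such woman would be 10% of an expected arm of 10. Their number may be zero and the direction of bias is unknown. The 1 to 15 mg/dL shifts above rest wholly on assumed inputs; they are illustrations, not estimates, and the 10 mg/dL figure is a rule for stratifying analyses, not an effect size. In an unpowered, non-randomized pilot this is a worthwhile, inexpensive correction that removes one avoidable source of confounding and leaves the larger one, Apple device ownership, in place.

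**What to change.** - Reconcile the Group 1 definition across the opening summary, the recruitment section, the treatment-group section and the *Statistical Analysis Plan*.
- Record CGM brand for every woman. The baseline questionnaire in Appendix B asks about CGM use but not the maker.
- Restrict the comparison of Dexcom alone with Dexcom plus Share to Dexcom users, and report non-Dexcom CGM users separately.
- Keep those women in comparisons of any CGM without Share against no CGM. State that comparison explicitly, and add a sensitivity analysis of Group 1 against Group 3 without them.

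An equivalent alternative is to rename Group 1 as any CGM without Share and to pre-specify the Dexcom-only analysis as a sensitivity analysis.

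The work is a brand field in the database and a few sentences of text. The statistical cost of the restriction, if 2 to 3 of 10 women are removed, is a standard error for Group 1 against Group 2 that is about 8 to 13% wider, or about 11 to 18% wider with 8 v 16 completers. If no such women enrol, it costs nothing.

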A total of up to 40 pregnant women will be prospectively recruited into the study. As this is an 'open-label' study whose group stratification is based on subject characteristics (willingness to wear CGM, subject possession of iPhone, iPad, or iPod touch, follower possession of iPhone, iPad, or iPod touch), we cannot predict the number of subjects per treatment arm. Based on our current pregnant population's willingness to use CGM and device usage, we anticipate that 10 subjects will be in Group 1, 20 subjects in Group 2, and 10 subjects in Group 3. We will include up to 30 additional women in Group 3 identified through a retrospective chart review who were pregnant around the time of study enrollment and before the study began.

In addition, there will one main follower for each prospectively enrolled pregnant subject (up to 40 adults) who will be asked questions once per month about knowledge of the subject's glucose trends and interventions that s/he may have done on her behalf over the last month.

What is the schedule of events for the treatment groups?

After screening, when pregnancy is confirmed subjects will be stratified to Group 1, 2, or 3. Subjects in all groups will have similar study/clinic visits for data acquisition at the screening, pregnancy visits (which occur a minimum of monthly throughout gestation), and post-partum clinic visit. All subjects will be required to test blood glucoses at least 7 times a day throughout pregnancy. All subjects will be asked to log the SMBG values 7 times a day with insulin doses for meals for 1 week every trimester of the pregnancy.

Subjects stratified to CGM wear will be provided with a Dexcom G4 CGM, transmitter, and sensors (4 per month). Subjects stratified to CGM wear who want to use their personal Dexcom G5 devices will be asked to provide Dexcom mobile usernames (if they use G5 with an iPhone) and will be provided with sensors (4

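### Up to three-quarters of the planned no-CGM arm comes from an undated chart review, and the SAP neither separates nor adjusts for control source

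*Combined protocol and SAP*

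**What the plan says.** The opening summary explains how prospective controls arise: "CGM use will be offered to all subjects, but individuals who do not want to wear a CGM will be stratified to Group 3". The section on the schedule of events for the treatment groups adds that the study supplies device, transmitter and sensors to those who accept.

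The section on subjects per arm anticipates that "10 subjects will be in Group 1, 20 subjects in Group 2, and 10 subjects in Group 3", and then: "We will include up to 30 additional women in Group 3 identified through a retrospective chart review". The section on treatment groups puts them in the same arm: "we will include pregnant no CGM users identified through a retrospective chart review into the no CGM arm of the study". The study population section describes them as "women who were pregnant around the time study enrollment began and earlier". The sections on arm size and on the control arm are similar, and none gives an earliest date.

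The Statistical Analysis Plan section compares outcomes within women over time and between arms, using linear mixed models. It does not mention the chart-review women. It names no control-source term, calendar term or baseline covariate, and no analysis restricted to prospective women. The weakness section admits that the study is not randomized, and puts this down to device compatibility. It mentions neither retrospective controls nor refusal.

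**The concern.** The no-CGM comparison is part of the study's stated goal. As written, its control arm mixes two kinds of women. One kind was offered CGM in the study, declined it, and is followed prospectively. The other was found afterwards in the record, was selected on not having used CGM throughout pregnancy, and may have been pregnant some years earlier. Every CGM user is prospective.

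A difference between sources in period, selection or data collection can therefore look like a CGM effect. Collection does differ for the glucose measures: prospective women are asked for structured one-week SMBG profiles each trimester, while chart-review women have whatever meter downloads exist. A single pooled contrast would also hide any disagreement between the two control sources.

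**Working it through.** **Plan's own figures.** 10 + 20 + 10 = 40 prospective women. With 20% drop-out, 40 × 0.80 = 32 completers, as the SAP states. The chart-review women are outside this count.

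**Share of controls.** Group 3 = 10 + 30 = 40, so chart review supplies 30/40 = 75%. With proportional drop-out among prospective women it is 30/(8 + 30) = 79%. The share falls if fewer than 30 are found and rises if fewer than 10 women decline.

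**What enters the pooled contrast.** Let S be the chart-review difference, and R the decliner difference, from what CGM women would have shown without CGM, both in the analysed quantity. With equal weight per woman and no CGM effect:

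- apparent effect = 0.75 × S + 0.25 × R.
- To match the 0.3-point A1C reduction in the SAP with R = 0, S must be 0.30/0.75 = 0.40 points. This is a conversion, not an estimate of S.

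**Level or change.** The SAP's A1C sentence can be read as change from first-trimester baseline. If the source difference is d1 at baseline and d2 later, the bias in change is 0.75 × (d2 − d1). A stable difference (d1 = d2) gives zero. In practice it would largely, not exactly, cancel, because women who start higher may change more.

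**What a source term would do.** Fit intercept, CGM and source to 30 CGM women, 10 decliners and 30 chart-review women. The chart-review women then inform only the source coefficient, and the CGM coefficient is CGM minus decliners.

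- Pooled SE: √(1/30 + 1/40) = 0.242 SD.
- With source term: √(1/30 + 1/10) = 0.365 SD, and 0.365/0.242 = 1.51.
- The documents give no A1C SD. For an assumed 0.6 to 1.2 points, the 95% half-width goes from 0.28–0.57 to 0.43–0.86 points.

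**Refusal.** Adding a refusal indicator gives four columns of rank three, because every prospective woman without CGM is a decliner. As an illustration with assumed S = 0.40 and R = 0.30, the pooled bias is 0.75 × 0.40 + 0.25 × 0.30 = 0.375. With a source term 0.30 remains, all of it refusal.

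**Scope.** Chart-review women completed no study questionnaires, so the between-arm fear-survey comparison rests on the roughly 10 prospective decliners and is untouched by pooling.

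**The case against.** The strongest reply is that the text does not settle pooling. The control-arm section introduces the chart-review women as a further control arm, and the SAP never says how they enter. That ambiguity is real. But two sections place them in Group 3, and the SAP compares study arms, so following the plan as written pools them.

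Other points stand in part. The window overlaps enrollment, and it is limited in practice by what the electronic record holds and by the need to contact and consent these women, so era confounding is partial. Prospective Group 3 receives usual care, so the contrast in clinical care is smaller than the contrast in data collection. This is also a pilot that declares itself non-randomized and without formal power. It still applies a 0.05 significance threshold and is meant to inform a larger study.

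A reader might infer three stronger claims that the documents do not support:

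- **A numerical A1C bias.** Assuming drift of 0.05–0.10 points a year and a lag of 2–6 years gives 0.75 × 0.05 × 2 = 0.075 to 0.75 × 0.10 × 6 = 0.45. Neither input is in the documents, and a drift in level largely cancels in change from baseline.
- **That the missing source or calendar term causes the refusal confounding.** No such term could remove it, as the rank check shows.
- **That comparing the two control sources is the only internal check available.** Pre-conception A1C by source, and concurrent against earlier chart-review women, are also checks.

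**Conclusion.** The concern holds for A1C, meter-download glucose measures and chart outcomes. At planned sizes up to 75% of controls differ from all CGM women in source and partly in era, and the SAP neither separates nor adjusts for this. Up to three-quarters of any source difference in the analysed quantity passes into the pooled contrast. This assumes that all 30 chart-review women are included, that 10 women decline, and that women are weighted about equally. The direction and size of the difference are unknown. Refusal is a separate limitation of the design that better modelling of source will not cure.

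**What to change.** - **Arm-size and control-arm sections:** state a start date for the look-back and a consecutive selection order. The length is for the sponsor to choose.
- **SAP, contrasts:** report CGM versus prospective Group 3 and CGM versus chart-review Group 3 separately with confidence intervals. Give the pooled estimate only beside both.
- **SAP, adjustment:** adjust these models for pre-conception or first-trimester A1C and for other baseline variables available from both sources, such as pump or MDI use and diabetes duration. Pre-conception A1C is already collected for both sources, and first-trimester values may include some CGM wear. Add year of conception as a sensitivity analysis.
- **SAP, what to avoid:** do not rely on a source term in one pooled model, since the CGM effect would then rest on about 30 versus 10 women.
- **Weakness section:** state that refusal cannot be separated from CGM use among prospective women.

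The cost is mostly wording, since dates and baseline values come from the chart. The downsides are a wide interval for the prospective-only contrast (SE about 1.5 times the pooled one), few baseline terms that so small a comparison can carry, and possibly fewer eligible chart-review women.
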